**b. Procedure Risks**

Testing this device in human patients is necessary to establish its feasibility in a clinical setting. Identifying a safe, quicker method for obtaining peritoneal access has the potential to improve care for patients.

---

**c. Use of Deception in the Study**

No deception will be used.

---

**d. Use of Audio and Video Recordings**

Non-identifiable digital photos and/or videos will be taken of the TPAD during use and post-operatively. Acquired digital images may capture a portion of the patient's skin, however if a patient has any identifying features such as scars or tattoos, these areas will be cropped out of the images, or if this is not possible, no images will be recorded of that patient. Images will be kept on an encrypted, secure server, accessible only to study personnel. Some of these images may be used for publication or shared with the sponsor for providing instruction for other surgeons. Any images not used for these purposes will be erase.

---

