### a. Procedures

Surgeons will identify patients scheduled to undergo laparoscopic surgery procedures and notify study staff. The patient will be met in the pre- operative holding area and informed consent will be obtained.

Patients will be randomized via block randomization.

Clinical information will be collected from participating patients including age, sex, demographic, past medical and surgical history, medications, allergies, diagnosis, and planned procedure. Clinical data will be de- identified and stored on a password protected spreadsheet on a PHI- safe server.

The surgeon will utilize the TPAD device to assist with Veress needle insertion (standard of care) to obtain access to the peritoneal cavity. The device will also be used to guide primary trocar placement.

Following induction of general anesthesia, the patient is prepped and draped in sterile fashion. Local anesthetic is infiltrated at the planned incision site and an incision is made with a scalpel. These steps are the same in any laparoscopic procedure. Next, the sterile TPAD, which is connected to a suction source, is centered over the incision, and the suction cups activated to non-invasively grasp the skin. The TPAD is pulled upward, and the Veress needle is advanced through the incision into the peritoneal cavity. Once the needle enters the cavity, the abdomen is insufflated as per usual standard of care. Once insufflated, the veress needle is withdrawn while maintaining the TPAD's suction on the skin. The primary trocar is then advanced through the incision into the abdominal cavity. The suction is then released and the TPAD taken away from the operating field.

The time needed to obtain laparoscopic access and the time needed for trocar placement will be recorded. Non-identifiable photos and/or video may be taken of the TPAD device during use. Acquired digital images may capture a portion of the patient's skin, however if a patient has any identifying features such as scars or tattoos, these areas will be cropped out of the images, or if this is not possible, no images will be recorded of that patient. There will be no other alterations to the planned surgery and it will proceed as planned. Following surgery, the surgeon will complete a questionnaire. Any adverse events will be recorded by medical record review.

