Patients will undergo routine postoperative care as indicated by their surgery. no additional visits will be required due to their being enrolled in the study. The patient will participate in a questionnaire and may take non-identifiable photographs of the portion of the patients skin where the TPAD device acts, as described above.

---

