**c. Procedures to Minimize Risk**

Risks will be minimized by adhering to the inclusion/exclusion criteria.

Postoperatively, patients will be cared for by the Stanford general surgery service which has expertise in the management of patients undergoing laparoscopic surgery.

All clinical data and images will be stored on an encrypted server. If the patient has identifying scars or tattoos, this will be cropped out of the images, or, if this is not possible, no images will be stored for that patient. All data will be coded with an assigned study number. The study key will be kept in a password protected file that will be deleted at the conclusion of the study.

---

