Pilot Study to Establish Safety and Ease of Use of a TauTona Pneumoperitoneum Assist Device (TPAD) for Laparoscopic Surgery

NCT04392635

August 19, 2024

Statistical Analysis Plan

Statistical Methods

For surgeon and patient questionnaire answers, a Wilcoxon test will be performed for each answer against a theoretical median of 4.0 (best). Since the insertion of the Veress needle should not significantly impact the final outcome of the entire laparoscopic procedure, analysis assumes that the theoretical median for each answer should be 4.0. Further, the standard of care is assumed to provide the current best care, so its theoretical median should be 4.0.

Determination of Sample Size

There were no statistically powered sample size requirements for this study. Based on the end points, the sample size of 15 for each group would be sufficient to determine bruising and the ability of the TPAD device to function as intended as compared to the control group.

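### Post-operative skin images may be erased without being scored for bruising, leaving the one listed device harm to unstructured chart review

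*Protocol*

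**What the plan says.** Protocol section 2.d plans images both during device use and afterwards: "Non-identifiable digital photos and/or videos will be taken of the TPAD during use and post-operatively". It then gives the permitted uses: "Some of these images may be used for publication or shared with the sponsor for providing instruction for other surgeons". The next sentence is "Any images not used for these purposes will be erase". No time of erasure is given. Safety assessment and source verification are not among the uses.

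Protocol section 2.a is looser about whether images exist at all. For the operation it says "Non-identifiable photos and/or video may be taken of the TPAD device during use". For the period after surgery it says study staff "may take non-identifiable photographs of the portion of the patients skin where the TPAD device acts". Where identifying marks cannot be cropped out, section 2.d adds "if this is not possible, no images will be recorded of that patient".

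Bruising appears in two other places. Section 9.a lists it, with discoloration, as the only risk of the TPAD itself, separately from the risks of Veress needle entry and of laparoscopy. The SAP, under Determination of Sample Size, says "the sample size of 15 for each group would be sufficient to determine bruising" and refers to a comparison with the control group.

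The stated source for adverse events is medical record review (section 2.a). Section 2.g makes adverse event monitoring a secondary outcome but does not name bruising. The SAP's Statistical Methods cover only questionnaire answers.

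**The concern.** In a small pilot of device safety, the harm specific to the device deserves a deliberate record. The post-operative pictures of the treated skin are the only direct view of that harm that the study itself is described as producing. Whether one survives depends on its use in a paper or in teaching, not on what it shows about safety.

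If images are erased unread, the bruising count depends on whether someone on the routine surgical service happened to write down a mild, short-lived skin mark. Under-recording is then possible, and for the patients concerned the chart count cannot be checked against a picture. Erasure is irreversible, so the gap cannot be closed later.

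**Working it through.** **No figure in the plan can be reproduced.** The SAP gives 15 per group with no alpha, power, bruising rate or margin, and says that the study was not powered. The point rests on reading the sections together.

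**Routes by which a bruise could enter the results**

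| Route | Where | What is specified | What is not |
|---|---|---|---|
| Chart review of adverse events | Protocol 2.a | Source is the medical record | Bruising definition, grading, assessor, time point |
| Post-operative skin image | Protocol 2.a, 2.d | May be taken; kept if used for publication or instruction | Scoring; retention as source; time of erasure; any control-arm image |
| Surgeon and patient questionnaires | Protocol 2.a, 2.g; SAP | Answers tested against a median of 4.0 | Item content, so a bruising question cannot be assumed |
| Study follow-up visit | Protocol 2.a, 9.d | None; participation ends with surgery | Not applicable |

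Only the image shows the skin directly, and it is the route with an erasure rule attached. The chart route is permitted but unstructured.

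**Scale, under stated assumptions.** The device arm is 10 in Protocol sections 1.a and 2.g and 15 in the SAP, so both are shown.

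1. *Weight of one missed case.* Change in the observed rate = 1/n: 1/10 = 10 percentage points; 1/15 = 6.7 percentage points.

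2. *Number of cases to be expected.* The documents give no bruising rate, so a range is assumed. P(at least one case) = 1 − (1 − p)^n.

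| Assumed true rate p | n = 10 | n = 15 |
|---|---|---|
| 5% | 40% | 54% |
| 10% | 65% | 79% |
| 20% | 89% | 96% |
| 30% | 97% | >99% |

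At the lower rates an arm with no cases at all is quite possible. An observed zero has a one-sided 95% upper limit of 1 − 0.05^(1/n), which is 25.9% for n = 10 and 18.1% for n = 15. Those limits hold only if every case was recorded.

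3. *Share of device patients whose chart entry could no longer be checked against an image.* Assume that every device patient is imaged, that m patients' images are kept and that the rest are erased unscored. The share is (n − m)/n.

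| Patients with images kept, m (assumed) | n = 10 | n = 15 |
|---|---|---|
| 3 | 70% | 80% |
| 5 | 50% | 67% |
| 8 | 20% | 47% |

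This is loss of verification, not an estimate of bias. It falls to zero if every image is scored and kept until the report.

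**The case against.** The best defence is that no section makes the images the bruising record. The stated source is the medical record, the photographs are optional, and erasing unused pictures suits the privacy purpose of a section on recordings. All of that is correct, so the erasure rule is not in itself a statistical error. It does not remove the gap: the chart route has no bruising item, and nothing requires a look at the pictures before they go. Privacy does not call for erasure before scoring either, since the images are non-identifiable and held on an encrypted server.

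A second objection is that the larger fault lies upstream, in the missing definition, assessor, time point and both-arm assessment. This stands. Keeping images cannot by itself deliver the comparison with control in the SAP, because the skin photographs described are of the area where the device acts.

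Three stronger readings are tempting and should be resisted:

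- A reader might infer that bruising cannot be determined at all. It can: chart review could yield a count, and with no erasure time stated, staff could score the images first.
- A reader might infer that images will be chosen to show clean skin. Nothing says so, and a report on bruising might equally show the bruised cases.
- A reader might take the rule on the study key, "The study key will be kept in a password protected file that will be deleted at the conclusion of the study", as closing off queries. Section 8.m lists a month of data analysis under the planned duration, so the key is not shown to be lost while queries are still open.

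**Conclusion.** The point holds as a gap in how the plan captures and keeps evidence. Images of the treated skin may be erased without being scored or held as source, while the only stated ascertainment of bruising is chart review without a structured item. The consequence is a count that may rest on incidental notes and that cannot be checked against erased images. It is not that bruising cannot be counted, nor that images will be selected for their appearance.

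Its size is not known from the documents. One missed case is worth 6.7 to 10 percentage points in the device arm. The share of patients without a checkable image depends on how many are imaged and kept, which the plan does not say; the shares of 20% to 80% shown above rest on assumed numbers. The point loses its force if the questionnaires or case form already contain a bruising item with a set time point, or if images are scored in practice before erasure. Neither is stated. The change is worth making because it is cheap and must come before any deletion.

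**What to change.** In Protocol section 2.d, add before the erasure sentence: *Every post-operative image of the treated skin is scored for bruising (present or absent, and extent) on the case form before any image is erased. All such images are kept until the final analysis and report are complete.*

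In the SAP, state that the report will give the number of device patients imaged and the number with bruising on images, alongside the chart-review count.

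Also state that the image-based count describes the device arm only, because images are optional, are not taken when identifying features cannot be cropped out, and are not described for controls. Any comparison with control needs one bruising item, with the same definition, assessor and time point, recorded in both arms.

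Cost: one case-form field, a short scoring task for study staff, and somewhat longer storage of coded, non-identifiable images on the existing encrypted server. Recording the item in controls is a further small task, needed only if the comparison in the SAP is kept.

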**e. Alternative Procedures or Courses of Treatment**

The alternative is to not participate. No standard treatments will be withheld as a result of participating in the trial. Typically, surgeons use a Veress or Hasson technique to obtain laparoscopic peritoneal access. The risks and benefits are the same for all laparoscopic access techniques. The benefit of laparoscopic surgery over open surgery includes smaller incisions/scars, less postoperative pain and faster recovery, and reduced risk for incisional hernia

---

**f. Will it be possible to continue the more (most) appropriate therapy for the participant(s) after the conclusion of the study?**

Yes

---

**g. Study Endpoint(s)**

The study will terminate after 10 patients have been enrolled and have undergone surgery with use of the study device and 10 patients have undergone the standard of care and completed the survey. The primary outcome measure is device feasibility as measured by a surgeon questionnaire, which is completed at the end of every surgery. Secondary outcome measures include the time needed to obtain laparoscopic access using the device, as well as monitoring for adverse events. Another secondary outcome measure includes patient questionnaire to assess satisfaction.

If there is clear evidence of a lack of device feasibility through surgeon questionnaire review, or if there are any adverse events recorded that are related to the device and which endanger the health of a patient, the project leader will evaluate this information and decide whether any modifications or termination of the protocol are indicated.

---

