### a. Brief Summary

The purpose of this study is to assess the safety and ease of use of a trocar placement access device (TPAD, Tautona) for laparoscopic surgery. 10 patients will undergo laparoscopic surgery as planned, with their surgeon using the TPAD device to guide Veress needle insertion and primary trocar placement while gaining access to the peritoneal cavity. Surgeons will complete a questionnaire following use of the TPAD to evaluate the device feasibility. Ten patients will undergo standard of care without use of the TPAD device and also complete surveys.

---

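### The study ends on a count of device uses rather than of randomised patients, so device non-use can drop out of the feasibility result

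*Protocol*

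**What the plan says.** Protocol section 2.a (Procedures) states: "Patients will be randomized via block randomization". Consent is taken in the holding area, before the device is tried.

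Protocol section 2.g (Study Endpoint(s)) sets the end of the study by what happens in theatre and afterwards. For the device group the condition reads: "The study will terminate after 10 patients have been enrolled and have undergone surgery with use of the study device". For the control group, the matching condition in the same sentence is that "10 patients have undergone the standard of care and completed the survey". That section also makes device feasibility the primary outcome, measured by a surgeon questionnaire filled in after each operation. The Brief Summary (section 1.a) describes the device group in similar terms: "10 patients will undergo laparoscopic surgery as planned, with their surgeon using the TPAD device".

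The SAP specifies one test, a Wilcoxon test of each questionnaire answer against a theoretical median of 4.0. Its sample-size paragraph says "There were no statistically powered sample size requirements for this study" and describes the purpose as judging bruising and "the ability of the TPAD device to function as intended as compared to the control group".

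Neither document defines use of the device, states whether patients may be replaced, names an analysis set, or says how a questionnaire is handled when the device was not used.

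**The concern.** Randomisation fixes who belongs to each arm before anything is known about how the device performs. Section 2.g then counts device patients by an event after that point. A patient allocated to TPAD whose surgeon goes straight to usual entry does not satisfy the condition, so recruitment continues and another patient can fill the place.

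In many trials this would be a small matter of bookkeeping. Here the question is whether the device can be used and works as intended, so a decision not to use it, when made for reasons to do with the device, is itself evidence on the primary outcome. A set of patients selected on device use is partly selected on the answer. With about 10 patients in the arm, one or two such cases would change the picture noticeably.

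The undefined term adds a second problem. If suction is applied, does not hold, and the surgeon reverts to usual entry, someone must decide whether that was use, and the plan leaves the decision until after the result is known.

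**Working it through.** **Step 1. The plan's own figures.** There is no powered sample size to reproduce: the SAP gives no alpha, power, effect size or dropout rate. The stated sizes are:

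- Protocol sections 1.a and 2.g: 2 × 10 = 20.
- SAP: 2 × 15 = 30, which equals the planned enrolment of 30 in Protocol section 8.a.

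**Step 2. The stopping rule applied to four possible cases allocated to TPAD.**

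| Case | Advances the section 2.g count? |
|---|---|
| Device applied, entry achieved with it | Yes |
| Device applied, attempt abandoned | Unclear; use is not defined |
| Device never applied, operation goes ahead | No, on the literal text |
| Operation cancelled or changed | No |

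The third row is the clear gap and the second is the ambiguous one. The fourth says nothing about the device.

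**Step 3. Illustration of size.** Let k be the number of TPAD patients replaced before 10 uses are reached. The documents give no value, so k is an assumption. Use among counted patients is always 10/10. Use among those randomised to TPAD is 10/(10 + k). The exact (Clopper-Pearson) 95% limits, treating the number randomised as fixed, are the 0.025 quantile of Beta(10, k + 1) and the 0.975 quantile of Beta(11, k), with an upper limit of 1 when k = 0.

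| k (assumed) | Counted | Randomised | Exact 95% CI, randomised |
|---|---|---|---|
| 0 | 10/10 | 10/10 = 100% | 69–100% |
| 1 | 10/10 | 10/11 = 91% | 59–99.8% |
| 2 | 10/10 | 10/12 = 83% | 52–98% |
| 5 | 10/10 | 10/15 = 67% | 38–88% |

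**Step 4. How readily replacement would arise.** Let f be the share of TPAD-allocated patients in whom the device is not used, also an assumption. Stopping at 10 uses gives an expected 10/(1 − f) patients randomised to TPAD, and the chance of at least one replacement is 1 − (1 − f)^10.

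| f (assumed) | Expected number randomised to TPAD | Chance of at least one replacement |
|---|---|---|
| 0 | 10.0 | 0% |
| 5% | 10.5 | 40% |
| 10% | 11.1 | 65% |
| 20% | 12.5 | 89% |
| 1/3 | 15.0 | 98% |

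Even a low non-use rate makes at least one replacement quite likely under the literal rule. At zero there is no effect.

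**The case against.** The strongest reply is that section 2.g says when the study stops, not who is analysed. No sentence in either document says that patients are replaced or left out. The surgeon questionnaire follows every operation, which on its face includes those where the device failed. The SAP tests each answer and excludes nobody. Section 2.g also foresees unfavourable questionnaires, since clear evidence of poor feasibility triggers a review by the project leader. All of this stands, and it is why overstatement is a possibility and not a finding. It does not close the gap: collecting a form does not settle whether it is analysed, and a form from a case without the device may carry no usable rating of it.

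It is also fair to say that a device applied and then given up has been used in the ordinary sense. That narrows the clear gap to patients in whom it was never applied, but leaves the abandoned case to judgement.

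Four stronger readings are tempting and are not supported:

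- **That 30 enrolled against 20 counted is an allowance for uncounted patients.** The SAP's 15 per group accounts for the 30 exactly. The difference is a separate inconsistency in sample size.
- **That the two arms are counted by different conditions.** The survey condition in section 2.g can be read as applying to both groups, and section 1.a says of the controls "Ten patients will undergo standard of care without use of the TPAD device and also complete surveys", where the word also suggests that both arms complete them.
- **That a planned comparison between arms is invalidated.** The only specified test is one-sample, against 4.0. The comparative phrase is in the sample-size paragraph.
- **That the trial would report 10/10.** No success proportion is planned, and a device that was used can still be rated poorly.

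**Conclusion.** The concern holds as a gap in the plan. Completion is tied to device use after randomisation, use is undefined, and nothing fixes the analysis set or rules out replacement, so the feasibility result can be overstated. The documents do not show that it is.

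The size depends wholly on a non-use rate that they do not give. The effect is nil if no device is left unused; in the illustration, 2 replacements separate 100% from 83%, and 5 separate 100% from 67%. These proportions show the direction and scale of the selection only, and do not measure bias in the questionnaire scores. The point is worth correcting because non-use is part of what feasibility means and the correction is cheap.

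**What to change.** 1. In Protocol section 2.g, end the study when the planned number has been randomised to each arm, without replacement for device non-use. First reconcile 10 and 15 per group so that there is one planned number.
2. In the SAP, state that all randomised patients who undergo laparoscopic entry are analysed in their allocated arm. Define use and abandonment, and say how the questionnaire is handled when the device was not used.
3. On the existing surgeon form, record whether the device was applied, whether suction held through entry, whether entry was achieved by the allocated method, and the reason for any non-use.
4. Report device success as n/N randomised to TPAD with an exact 95% CI, as a descriptive measure beside the questionnaire. Show non-use unrelated to the device, such as a cancelled or changed operation, separately so that it is not taken for device failure.

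The cost is some wording, a few tick boxes, and a feasibility figure that may look less favourable. The primary questionnaire measure is unchanged.

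### Neither document states what questionnaire result counts as device feasibility, the primary outcome, and the planned Wilcoxon test against the best score cannot supply it

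*Protocol*

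**What the plan says.** Protocol section 2.g, Study Endpoint(s), defines the primary outcome: "The primary outcome measure is device feasibility as measured by a surgeon questionnaire, which is completed at the end of every surgery". The same section asks the project leader to evaluate the information and decide on modification or termination "If there is clear evidence of a lack of device feasibility through surgeon questionnaire review", or on certain device-related adverse events. It attaches no score, item, proportion of uses or other criterion to feasibility or to its lack.

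The SAP, under Statistical Methods, gives one analysis for the surgeon and patient questionnaires: "a Wilcoxon test will be performed for each answer against a theoretical median of 4.0 (best"). It explains that "analysis assumes that the theoretical median for each answer should be 4.0", and for the control arm that "the standard of care is assumed to provide the current best care, so its theoretical median should be 4.0". It states no significance level, sidedness, method of computing the p-value, rule for combining answers, or interpretation of either test result.

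On numbers, section 2.g has "The study will terminate after 10 patients have been enrolled and have undergone surgery with use of the study device". The SAP, under Determination of Sample Size, says "There were no statistically powered sample size requirements for this study" and then that "the sample size of 15 for each group would be sufficient to determine bruising and the ability of the TPAD device to function as intended" relative to control.

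**The concern.** The primary outcome is feasibility, yet a reader with the complete data set could not tell from either document whether the device had been shown feasible. In a small unpowered study, a criterion fixed in advance is the main guard against a conclusion chosen after the ratings are seen.

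The planned test does not fill the gap. The result the sponsor hopes for, a median at the best score, is the null hypothesis, so the test can only fail to contradict it. Failing to reject in 10 or 15 uses is weak evidence of anything. Because the reference value is the top of the scale, the exact test also counts below-best answers without regard to how poor they are. For a feasibility question, one step below best and the bottom of the scale are very different answers. Missing forms can only lower that count, and so make a non-significant result easier to reach.

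**Working it through.** **Inputs.** Reference value 4.0, labelled the best score (SAP, Statistical Methods). Device uses: 10 (protocol 2.g) or 15 (SAP, Determination of Sample Size). Assumed because not stated: two-sided 0.05; one answer examined at a time; answers of 4 dropped as zero differences (the Pratt handling of zeros gives the same exact p-values). The bottom of the scale is not given, but the exact result does not depend on it.

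**The plan's own figure.** The SAP's 15 per group cannot be reproduced: it comes with no alpha, effect size or power.

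**Exact test.** No answer can exceed 4, so every non-zero difference is negative and the positive-rank sum is 0. With k answers below 4, only one of the 2^k sign patterns is as extreme in that direction. Hence one-sided p = 1/2^k and two-sided p = 2/2^k. Neither the size of the shortfalls nor n enters.

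**Normal approximation, all k shortfalls identical.** Every rank is (k+1)/2, the mean is k(k+1)/4 and the tie-corrected standard deviation is √k(k+1)/4. So z = √k without continuity correction, and z = √k − 2/[√k(k+1)] with it. For k = 4 this gives z = 2.00 (p = 0.0455) and z = 1.80 (p = 0.072).

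| k below best, all equal | Exact two-sided | Normal, no correction | Normal, corrected | Share of 10 | Share of 15 |
|---|---|---|---|---|---|
| 3 | 0.25 | 0.083 | 0.149 | 30% | 20% |
| 4 | 0.125 | 0.0455 | 0.072 | 40% | 27% |
| 5 | 0.0625 | 0.025 | 0.037 | 50% | 33% |
| 6 | 0.031 | 0.014 | 0.020 | 60% | 40% |

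The largest number of identical worst scores that stays non-significant is therefore 5 (exact two-sided), 4 (normal with correction) or 3 (normal without correction). For the exact one-sided test it is 4, since k = 4 gives 0.0625 and k = 5 gives 0.031.

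**Ordering at one sample size, exact two-sided test.** Five worst scores with the rest at 4: p = 0.0625, not significant. Six answers one step below best with the rest at 4: p = 0.031, significant. If the scale runs 1 to 4 in whole numbers (an assumption), the means are:

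- n = 10: (5×1 + 5×4)/10 = 2.5 for the set that is not significant, and (6×3 + 4×4)/10 = 3.4 for the set that is.
- n = 15: (5×1 + 10×4)/15 = 3.0, and (6×3 + 9×4)/15 = 3.6.

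**The normal approximation does not repair this.** There the values matter through the ranks and ties, but not reliably in the right direction. On the same assumed scale and without correction, four answers of 3 give p = 0.0455, while the worse set 3, 3, 2, 1 gives 0.066.

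**How easily a non-significant result arises.** If each use independently has a true 50% chance of a below-best rating, the exact two-sided test is non-significant with probability P(k ≤ 5) = 0.62 at n = 10 and 0.15 at n = 15.

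**The case against.** The strongest reply is that the SAP contains no pass rule to criticise. It says a test will be done and never says that a non-significant result means feasible. That is correct. A reader might infer such a rule from the statement that the median should be 4.0, but it remains an inference, and the figures above are conditional on it. Rejecting the inference does not rescue the plan: no criterion is then left.

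A reader might also infer that the plan lets a device through with half its uses at the worst score. The documents do not support this as a general statement. It needs the protocol's 10 uses together with an exact two-sided test at 0.05. On the SAP's 15, five uses are one third. Five identical worst scores are significant under the one-sided exact test (0.031) and under the normal approximation (0.025, or 0.037 with correction).

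Second, this is a pilot, and describing ratings without a go/no-go mark is a legitimate pilot design. That has weight. But the SAP does not plan a description; it plans a test. It also asserts that its sample size suffices to determine whether the device functions as intended, a claim that cannot be checked without a criterion.

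Third, the questionnaire is not in the documents and may carry anchors that define acceptable use. That stands. It limits what can be proposed: neither the item, nor the meaning of a 3, nor any particular count can be prescribed from here.

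**Conclusion.** The point holds in a limited form. Neither document states what questionnaire result constitutes feasibility, and the phrase about clear evidence of its lack is not operational. The planned test cannot stand in for a criterion, because it places the hoped-for result in the null and, in exact form, ignores how low the ratings are.

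The size is conditional. If non-significance on a single answer at two-sided 0.05 were read as feasible, 3 to 5 uses at the worst score could pass, depending on how the p-value is computed. The upper end, five, is 5/10 on the protocol's number and 5/15 on the SAP's. The ordering failure (0.0625 against 0.031) needs no mixing of sample sizes, but it does rest on the exact two-sided test. This should be corrected. It does not show that the study would reach a wrong conclusion.

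**What to change.** In protocol section 2.g and the SAP:

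- State that a non-significant Wilcoxon result against 4.0 is not evidence of feasibility. If the test is kept, state alpha, sidedness and exact or approximate computation.
- Make the primary summary the number and proportion of TPAD uses rated acceptable on one named surgeon-questionnaire item. Define the acceptable categories from the questionnaire's own anchors, count a missing form as not acceptable, and report an exact one-sided 95% lower bound.
- Fix the required count before any ratings are reviewed. As illustration only, 13/15 has a lower bound of 0.64 and 9/10 of 0.61. The chance of reaching 13/15 is 0.027 if the true acceptable rate is 0.60 and 0.82 if it is 0.90; for 9/10 the chances are 0.046 and 0.74. The sponsor should choose the count to match the intended claim and the final number per arm.
- Refer to the same acceptable-rating definition in the section 2.g clause on lack of feasibility, leaving the resulting decision with the project leader as now. This gives the review a common measure but does not set a trigger.

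The cost is a few sentences, with no new data, patients or staff. The downside is that the sponsor commits to a mark the device could miss, and the claim becomes more modest: 13 acceptable uses of 15 would show only that the true rate is above about 64%.
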